3.5.2. Visit Schedule

A summary of the visit schedule and assessments is presented in [Table 2](#).

Table 2: Visit Schedule and Assessments

	Screening	Day 1 ^a (M)	Induction				Rest	Challenge (Week 6)				
			M 8, 15	Tu 2, 9, 16	Th 4, 11, 18	F 5. 12, 19		Week 4 & 5	M	Tu	W	Th
Informed consent	X											
Inclusion/Exclusion	X	X										
Medical history	X											
Demographic information	X											
Fitzpatrick Skin Typing	X											
UPT		X										X
MED irradiation/evaluation		X ^b										
Randomization		X										
Product application		X	X		X			X				
Application site evaluations			X ^c	X	X	X ^d			X	X	X	X
Application site irradiation				X		X ^d		X	X			
Make-up evaluation/application							X ^e					
Make-up evaluation/irradiation							X ^e					
Review of concomitant medications	X	X	X	X	X	X	X ^f	X	X	X	X	X
Review of AEs	X	X	X	X	X	X	X ^f	X	X	X	X	X

a Screening and the first day of Induction (Day 1) may take place on the same day.

b MED irradiation on Day 1 and MED evaluation on Day 2.

c The first Monday (Week 1) of the Induction Phase.

d Evaluations will not be conducted after irradiation on the last Friday of the Induction Phase. Untreated control site will also be irradiated.

e Make-up evaluation/application and evaluation/irradiation are performed as necessary (see [Section 3.5.1](#)).

f Concomitant medications and AEs will be reviewed only for subjects who are required to return to the test facility for make-up visits during Rest Period - Week 4.

Note: The visit schedule may be revised if necessary.

3.5.3. Definition of Minimal Erythema Dose

Minimal erythema dose (MED) is defined as the length (in time) of light exposure required to produce a minimal erythema reaction 16 - 24 hours after irradiation using a standardized filtered UV light source that emits UVB (290-320 nm) as part of its emission spectrum.²

3.5.4. Light source

The light source will be a Xenon Arc Solar Simulator (150 W), with UV-reflecting dichroic mirror, UVC-blocking filter, and visible/infrared blocking filter to generate a continuous emission spectrum in the UVA and UVB range (290 to 400 nm).² An additional filter is added during irradiation of the application sites to block UVB radiation allowing only UVA irradiation of the sites. The output is measured daily prior to irradiation using a radiometer/photometer.

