Study Design:	During the 3-week Induction Phase, CCP-020 (Diacerein 1%) Topical Ointment and vehicle ointment, will each be applied 2 times per week (Monday and Thursday) to 2 sites on the infrascapular area of the back under fully occlusive patch conditions for approximately 24 hours (± 4 hours). Minimal erythema dose (MED) irradiation will also be performed for each subject on Day 1. After patch removal, all application sites will be evaluated and one application site of each study product will be irradiated with 2 times the subject's MED using the full Xenon lamp spectrum. All sites will be evaluated at approximately 48 hours later when irradiated on Tuesdays and 72 hours later when irradiated on Fridays. An additional application of study product may be applied on the Monday of rest week 4 if the subject misses an irradiation session during the induction phase of the study. At Challenge, CCP-020 (Diacerein 1%) Topical Ointment and vehicle ointment will each be applied once to 2 naive sites on the infrascapular area of the back under fully occlusive patch conditions for approximately 24 hours (± 4 hours). After patch removal, all application sites will be evaluated and one site of each test product will be irradiated with 6 J/cm^2 of Ultraviolet A (UVA) followed by 0.5 times the subject's MED of UVA/Ultraviolet B (UVB). An additional untreated site will also be irradiated at Challenge and will serve as an untreated control. Each site, including the untreated control site, will be evaluated again at approximately 24 hours (± 4 hours), 48 hours (± 4 hours), and 72 hours (± 4 hours) following irradiation. A Rechallenge will be performed if a cutaneous response observed during the Challenge Phase indicates possible photosensitization or at the discretion of the Investigator.
Planned Sample Size:	50 evaluable subjects
Study Population:	Healthy adult male and female volunteer subjects
Investigational Products:	CCP-020 (Diacerein 1%) Topical Ointment Vehicle Ointment
Control:	An untreated irradiated non-occlusive (open) control site.
Efficacy Evaluation Criteria:	Not applicable

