3. INVESTIGATIONAL PLAN

3.1. Study Design

This will be a randomized, double-blind, single-center, vehicle-controlled, within-subject comparison study of the study products, CCP-020 (Diacerein 1%) topical ointment, vehicle ointment, and an untreated irradiated non-occluded (open) control site. A total of 4 application sites (2 cm x 2 cm each) will be marked on the subject's back and distributed so that 2 sites are on each side of the back. One side of the back will be designated for irradiation after approximately 24 hours (± 4 hours) of study product application and the other side will remain non-irradiated. An additional site will be marked on the "irradiated side" of the back. The site will receive no study product, but will be irradiated at Challenge to serve as an untreated irradiated non-occluded control.

A defined area (approximately 50 cm²) on the infrascapular region of each subject's back will be irradiated to determine the minimal erythema dose (MED) of ultraviolet (UV) light.

During the 3-week Induction Phase, 0.2 mL of each study product will be applied to 2 sites twice each week (Monday and Thursday) for approximately 24 hours (± 4 hours) under occlusive patch conditions (6 applications). After patch removal, all application sites will be evaluated and one application site of each study product will be irradiated with 2 times the subject's MED using the full Xenon lamp spectrum. The sites will be evaluated by a trained evaluator. All sites will be reevaluated post irradiation, at approximately 48 hours later when irradiated on Tuesdays and at approximately 72 hours later when irradiated on Fridays except when irradiated on the last Friday of the Induction Phase or if a subject is taking a missed visit during induction, the sites will not be evaluated. These procedures will be performed each week for 3 weeks of the Induction Phase. Dermal reactions at the application sites will be evaluated using a visual scale that rates the degree of erythema, edema, and other signs of cutaneous irritation (see [Table 3](#) and [Table 4](#)).

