3.5. Visit Schedule and Assessments

3.5.1. Study Procedures and Visit Schedule

Screening

At Screening, the subjects will receive any necessary written and verbal information, and the informed consent of each subject will be obtained. Demographic data (including Fitzpatrick skin type) will be recorded, a medical history will be taken, and previous and concomitant medications will be reviewed. Eligibility will be determined by review of the inclusion/exclusion criteria.

- Any written and verbal information
- Informed consent
- Demographics
- Previous/concomitant medication
- Review of inclusion and exclusion criteria
- Medical history (including lifestyle and habits)
- Evaluation of application site area

Table 1: Fitzpatrick Skin Types

I	Always burns easily, never tans
II	Always burns easily, tans minimally
III	Burns moderately, tans gradually
IV	Burns minimally, always tans well
V	Rarely burns, tans very well
VI	Never burns, deeply pigmented ^{3,4}

Day 1

On Day 1, all subjects will be questioned regarding the entry criteria and female subjects of childbearing potential will undergo a UPT. If the subject fulfills all the inclusion and none of the exclusion criteria, he/she will be allowed participation in the study. Upon enrollment, each subject will be assigned a unique subject number and receive a randomization code, indicating application placement of the study products.

A baseline evaluation of the patch sites will be performed immediately prior to application of the patches to ensure that no conditions, markings, or coloration of the skin will interfere with interpretation of the study results.

A total of 4 application sites (2 cm x 2 cm each) will be marked on each subject's back, placing 2 sites on opposite sides of the back. The distance between the patches will be no less than one centimeter. The numbering of the test sites will remain the same throughout the study. The sites will be marked with an indelible, surgical marker.

Minimal Erythema Dose (MED) Determination

On Day 1, subjects will have an area of skin on their back, approximately 50 cm², divided into 6 equal sites marked with a surgical marker. Each of the sites will be irradiated with full spectrum UV light, with each exposure differing from the next by a factor of 1.25 (ie, each irradiated site will be exposed to a 25% greater dose of UV irradiation than the previous site).²

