The areas involved in MED determination will be different from the study product application sites. Evaluation of the exposed sites will be performed on Day 2.

Induction

The Induction Phase consists of a series of 4 patch applications of the study products and subsequent irradiation and evaluations of the patch test sites over a 3-week Induction Phase.

Under occluded conditions, 0.2 mL of each study product, CCP-020 (Diacerein 1%) topical ointment and vehicle ointment will be applied to two Webril® pads. The patches will be secured with nonporous plastic film adhesive bandage (Blenderm tape) and hypoallergenic paper tape (3M Micropore™), as needed. The patches will then be applied to their assigned sites on each side of the back for 24 hours (± 4 hours). This process will be repeated twice each week (Mondays and Thursdays) during the 3-week Induction Phase. The same study product will be applied to the same test site throughout the Induction Phase.

Application sites will be evaluated immediately prior to study product application.

After 24 hours (± 4 hours) of study product application (eg, Tuesday and Friday), all patches will be removed. The sites will be evaluated using the scoring system detailed in [Section 3.5.7.1](#). One side of the back will be assigned for irradiation and the other will remain non-irradiated, ie, only one application site of each study product will receive irradiation. On all Tuesdays and Fridays, the sites designated for irradiation will be irradiated with 2 times the subject's MED using the full Xenon lamp spectrum.

Adverse events and concomitant medications will be reviewed at each visit and recorded as applicable.

One application/irradiation session may be missed during the Induction Phase. It must be made-up during Week 4. An additional application of study product may be applied on the Monday of rest week 4 if the subject misses an irradiation session during the Induction Phase of the study. No evaluation will be required following the final irradiation during the challenge period.

Rest Period (Weeks 4 and 5)

During the Rest Period of approximately 10-17 days, subjects will not receive any application of study materials. An additional application of study product may be applied on the Monday of rest week 4 if the subject misses an irradiation session during the Induction Phase of the study.

Challenge (Week 6)

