On Day 1 of the Challenge Phase, subjects who have completed the Induction Phase and the Rest Period will have study product applications to naive sites in the same manner as applied during the Induction. A baseline evaluation of the naïve sites will be performed immediately prior to application of the patches to ensure that no conditions, markings, or coloration of the skin will interfere with interpretation of the study results. As in the Induction Phase, 0.2 mL of CCP-020 (Diacerein 1%) topical ointment and vehicle ointment will each be applied to 2 naive sites for approximately 24 hours (± 4 hours) under occlusive patch conditions. The clinical staff will then remove the patches and a trained evaluator will evaluate the test sites. There will be a main evaluator for the study; a backup evaluator will also be assigned in the event that an emergency occurs and the main evaluator is unable to attend the study visit. The designated sites and an additional untreated control site will be irradiated with 6 J/cm^2 of UVA (320-400 nm) followed by 0.5 times the MED of UVA/UVB (full-spectrum) irradiation, obtained by using a filtered light

source (see [Section 3.5.4](#)). Each site will be evaluated again at approximately 24 hours (± 4 hours), 48 hours (± 4 hours), and 72 hours (± 4 hours) post irradiation.

Adverse events and concomitant medications will be reviewed at each visit and recorded as applicable. A UPT will be performed for female subjects of childbearing potential at the last study visit.

Rechallenge

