A Rechallenge should be performed if a cutaneous response observed during the Challenge Phase indicates possible photosensitization or at the discretion of the Investigator. If it is determined by the Investigator that a Rechallenge should be performed, the Rechallenge patches will be applied as soon as Challenge reactions have resolved. Just as in the challenge procedure 0.2 mL of each study product CCP-020 (Diacerein 1%) topical ointment and vehicle ointment, will each be applied to 2 naïve sites for approximately 24 hours (± 4 hours) using appropriate patches to further discriminate a photosensitization reaction from an irritation reaction. A baseline evaluation of the naïve sites will be performed immediately prior to application of the patches to ensure that no conditions, markings, or coloration of the skin will interfere with interpretation of the study results. Approximately twenty-four (24) hours (± 4 hours) after study product application, the clinical staff will remove the patches and a trained evaluator will evaluate the test sites. One site of each product and an additional untreated control site will be irradiated with 6 J/cm² of UVA (320-400 nm) followed by 0.5 times the MED of UVB (290-320 nm) irradiation using a filtered light source. All sites (irradiated and non-irradiated) will be graded for dermal reactions at approximately 24 hours (± 4 hours), 48 hours (± 4 hours), and 72 hours (± 4 hours) following irradiation. Concomitant medications and AEs will also be reviewed.

End of Study

At the EOS, all patches will be removed as described above, and the final evaluations of the test sites will be made.

An EOS examination will be conducted and consist of the following:

- Concomitant medication
- AEs
- UPT in females of childbearing potential

Concomitant medications and AEs will be reviewed and recorded during the whole study. For a detailed listing of scheduled study time points refer to the Visit Schedule and Assessments ([Table 2](#)).

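### Section 3.5.4 puts a UVB-blocking filter on product-site irradiation without limit, contradicting the full-spectrum Induction doses and the UVB-containing second step at Challenge and Rechallenge

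*Combined protocol and SAP*

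**What the plan says.** Section 3.5.4 describes a xenon solar simulator that emits from 290 to 400 nm, covering both UVA and UVB. It then adds: "An additional filter is added during irradiation of the application sites to block UVB radiation allowing only UVA irradiation of the sites". No phase or step is attached to that sentence.

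The dosing instructions for the same sites are:

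- **Induction.** Section 3.1 says "one application site of each study product will be irradiated with 2 times the subject's MED using the full Xenon lamp spectrum". The Induction part of Section 3.5.1 repeats it for every Tuesday and Friday: "the sites designated for irradiation will be irradiated with 2 times the subject's MED using the full Xenon lamp spectrum". The Synopsis agrees.
- **Challenge.** Section 3.5.1 says the sites "will be irradiated with 6 J/cm^2 of UVA (320-400 nm) followed by 0.5 times the MED of UVA/UVB (full-spectrum) irradiation", and refers the reader to Section 3.5.4 for the filtered source. The Synopsis gives the same two steps.
- **Rechallenge.** Section 3.5.1 gives the same UVA dose, "followed by 0.5 times the MED of UVB (290-320 nm) irradiation using a filtered light source".

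The unit of dose also depends on UVB. For MED determination, Section 3.5.1 says "Each of the sites will be irradiated with full spectrum UV light". Section 3.5.3 defines the MED as an exposure time, found "using a standardized filtered UV light source that emits UVB (290-320 nm) as part of its emission spectrum".

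**The concern.** In a photoallergy study the light is half of what is tested. The protocol gives two incompatible instructions about its spectrum. In Section 3.1 the application sites are the product sites, and Table 2 has a single row for application site irradiation that spans Induction and Challenge. Someone setting up the lamp from Section 3.5.4 could therefore conclude that the MED test is done with the full spectrum and every product site is then irradiated with UVA alone.

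If that happened, the product sites would receive no UVB at any step and the prescribed multiples of the MED would not be delivered. Both irradiated product sites would be affected alike, so CCP-020 versus vehicle would not be biased. What would suffer is the sensitivity of the test, including the irradiated versus non-irradiated contrasts in Section 4.6.1. The clinical report would also state an exposure that differs from the one given.

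**Working it through.** The plan gives no figure to reproduce here, so the check compares every prescribed exposure of the product sites with the filter sentence.

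| Exposure | Source | Dose | Spectrum ordered | Possible with UVB blocked? |
|---|---|---|---|---|
| Induction, each session | Synopsis; 3.1; 3.5.1 | 2 × MED | Full lamp output | No |
| Challenge, step 1 | Synopsis; 3.5.1 | 6 J/cm² | UVA, 320–400 nm | Yes |
| Challenge, step 2 | Synopsis; 3.5.1 | 0.5 × MED | UVA and UVB | No |
| Rechallenge, step 1 | 3.5.1 | 6 J/cm² | UVA, 320–400 nm | Yes |
| Rechallenge, step 2 | 3.5.1 | 0.5 × MED | UVB, 290–320 nm | No |

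**Does any text limit the filter?** No. The Challenge text in Section 3.5.1 points to Section 3.5.4, but it does so after describing a sequence whose second step needs UVB. The word filtered does not identify the filter either, because the base lamp already has UVC and visible/infrared filters.

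**Number of steps in conflict.** Six Induction sessions follow from Section 3.1 (six applications), Section 4.3 (at least six) and the schedule of two a week for three weeks (2 × 3 = 6).

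- Scheduled steps: 6 Induction + 2 Challenge = 8. In conflict: 6 + 1 = 7.
- With a Rechallenge: 8 + 2 = 10 steps. In conflict: 7 + 1 = 8.

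**Prescribed UVB-containing exposure in conflict, per product.**

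- Induction: 6 × 2 MED = 12 MED.
- Challenge, step 2: 0.5 MED, so 12 + 0.5 = 12.5 MED.
- Rechallenge, step 2: a further 0.5 MED, so 13.0 MED.

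These totals add doses given to different skin, since Challenge and Rechallenge use naive sites. No single site is scheduled to receive 12.5 or 13.0 MED.

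The Induction text in Section 3.5.1 also mentions a series of four applications, which disagrees with its own schedule. With four sessions, the conflict covers 4 + 1 = 5 of 6 steps and 4 × 2 + 0.5 = 8.5 MED, or 6 of 8 steps and 9.0 MED with Rechallenge. The conclusion does not change.

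**Effect on the MED multiples.** Let *t* be a subject's MED, an exposure time on the lamp with UVB present. Induction prescribes 2*t* on that same output, and the second Challenge step prescribes 0.5*t*. Running those times behind a UVB-blocking filter removes the 290–320 nm part. The result is no longer 2 × or 0.5 × the measured MED, and the plan measures no MED on the filtered output. For Rechallenge step 2 as written, blocking 290–320 nm leaves nothing of the band ordered.

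**The case against.** The best reply is that the dosing text settles the matter in practice. Every statement of the Induction spectrum calls for the lamp's full output, and none mentions a UVB filter or Section 3.5.4. The Challenge text sets a UVA step against a full-spectrum step, a contrast that would be meaningless with the filter always in place. The only dosing instruction that refers to Section 3.5.4 is the one containing a UVA-only step. A careful reader who puts specific dosing instructions above a general equipment description reaches one workable reading. Nothing suggests that the single center would do otherwise. On this view it is a wording clarification, and the counts above measure wording and not harm.

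Much of this stands. The intent can be inferred, the worst case is unlikely, and the counts locate the conflict without predicting wrong doses. It is an internal inconsistency; no design decision is in dispute. But the inference is left to the reader. The protocol has no rule on which section prevails, and the Challenge text sends the reader to the conflicting sentence. Section 5.5.2 permits no deviations from planned conduct, yet a full-spectrum Induction dose departs from Section 3.5.4 and a filtered one departs from Section 3.5.1.

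**Conclusion.** The concern holds. As written, the filter sentence in Section 3.5.4 is irreconcilable with every Induction irradiation and with the second step at Challenge and Rechallenge: 7 of 8 scheduled steps, or 8 of 10 with Rechallenge, taking six Induction sessions. It should be corrected, because it is an operative instruction about the exposure under test.

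The clinical effect depends on how the site sets up the lamp. If the visit-level dosing text is followed, there is no loss. If Section 3.5.4 is followed literally, no product site receives UVB. The documents give no action spectrum for diacerein or rhein, so the resulting loss of sensitivity cannot be put in numbers. Whether the second Rechallenge step should be UVB alone or UVA with UVB is a separate question; the UVB-blocking filter must be out in either case.

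**What to change.** Reword the sentence in Section 3.5.4 to say that the UVB-blocking filter is used only for the 6 J/cm² UVA (320–400 nm) step at Challenge and Rechallenge. State that it is removed for:

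- the MED test;
- all Induction irradiations, including a Week 4 make-up session;
- the 0.5 × MED second step at Challenge and at Rechallenge.

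Recording filter status on the CRF at each irradiation is optional. It would let the report confirm the spectrum delivered.

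The cost is one wording change, made as a written amendment under Section 5.5.1. It adds no procedure, visit or subjects and alters no intended dose.

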3.5.5. Background information

Date of birth, gender, race, Fitzpatrick skin type (see [Table 1](#)), and a significant medical history of each subject will be recorded at Screening.

3.5.6. Efficacy Assessments

No efficacy will be assessed in this study.

3.5.7. Safety Assessments

3.5.7.1. Patch Test Site Evaluations

For both Induction and Challenge Phases, after 24 hours (± 2 hour) of product application, all sites will be evaluated and one application site of each product and the additional untreated site will be irradiated. The sites will be examined for dermal reactions at approximately 24 hours (± 4 hours), 48 hours (± 4 hours), and 72 hours (± 4 hours) post-irradiation.

The scores in [Table 3](#) will be used to express the response observed at the time of examination and will be recorded on the subjects' CRFs. The score will be used for statistical analysis. Additional response notations are presented in [Table 4](#).

Table 3: Response Scores

Response	Symbol	Numerical Equivalent Score
Erythema		
No reaction	-	0
Mild, but definite erythema	+	1
Moderate erythema	++	2
Marked/severe erythema	+++	3
Edema		
No reaction	-	0
Mild, but definite edema	**	1
Definite edema with erosion/vesiculation	***	2

Table 4: Notations

Response/Comment	Notation
Hyperpigmentation	Hr
Hypopigmentation	Ho
Vesiculation	V
Papular response	p
Papulovesicular response	pv
Damage to epidermis: oozing, crusting, and/or superficial erosions	D
Itching	I
Spreading of reaction beyond patch study site (ie, reaction where material did not contact skin)	S
Follicular irritation with or without pustule formation (folliculitis)	f
Subject absent	X
Patch dislodged	PD
Not patched	NP
No reaction	0

The readings will be made under a standardized white light source.

The 3-week period of patch contact during the Induction Phase may result in tape-related irritation in some individuals. Tape related irritation will not be graded as an irritant response at the patch site but will be noted separately on the CRF.

The Investigator will assess the reactions seen during the Challenge Phase and determine whether the subject is photosensitized or not. The following guidelines are generally considered in this assessment. Not all observations of erythema and edema are associated with photosensitivity; only if erythema and edema are observed can a reaction be suspected of being a positive photosensitivity reaction. An increase in the intensity of the reaction over time further

supports an assessment of photosensitivity. If reactions are observed at both the irradiated and non-irradiated study product sites (ie, if contact sensitization may have occurred), the reaction at the irradiated site upon Rechallenge must be at least one grade more intense than at the non-irradiated site for the reaction to be suspected of being a photosensitivity reaction (refer to [Section 3.5.7.1](#) for response scores and notations).

